### 6.2.12 PK Parameters

The following PK parameters will be calculated for DYN101:

$AUC_{\tau}$	Area under the plasma concentration-time curve during a dosing interval
$AUC_{last}$	Area under the plasma concentration-time curve from time 0 to time of the last quantifiable concentration
$AUC_{\infty}$	Area under the plasma concentration-time curve from time 0 to infinity
$C_{max}$	Maximum plasma concentration
CL	Clearance after IV administration
$\lambda_z$	Terminal disposition phase rate constant
$t_{1/2}$	Terminal disposition phase half-life
$t_{max}$	Time of first occurrence of $C_{max}$
$V_z$	Apparent volume of distribution during the terminal disposition phase

### 6.2.13 Pharmacodynamic data

#### Patient-Reported Outcomes Measurement Information System (PROMIS) Questionnaire

Summary T-score for each domain (Anxiety, Depression, Fatigue, Pain Interference, Ability to Participate and Physical Function) will be calculated. Scoring is done by calculating total raw scores for each domain by summing subject's answers. Missing values are not allowed and if any data missing for a domain then total raw score will not be calculated. After raw scores are calculated a scoring table will be used to translate the total raw score into a T-score for each subject. Scoring tables are shown in the [Appendix](#) of this document.

For Physical Function, NHS part of the study utilized different PROMIS scale. First question was ‘Can you walk 25 feet on a level surface (with or without support)?’. If subject answered ‘Yes’ then he/she filled all the following 12 questions. If subject answered ‘No’ then only 6 further questions were filled.

### **Respiratory Function Tests**

For each parameter, the attempt should be repeated at least 3 times making sure that the subject has recovered between attempts. If, at each attempt, there is an improvement in the results, further tests can be conducted until the subject has achieved his/her best result. For summary tables the best result will be selected.

For respiratory function tests ratio of FEV1/FVC will be calculated for each subject and visit and rounded to 1 decimal place.

### **6.2.14 Cumulative information for IDMC meetings**

The IDMC will review cumulative safety and PK and efficacy study data for all previously dosed subjects.

### **6.3 Conventions**

All data listings, summaries, figures and statistical analyses will be generated using SAS (Version 9.4 or higher).

Summary tables will be presented by treatment group. Treatment group includes information about dose (cohort) and mutated gene (subcohort).

PK data listings, summaries, figures, and statistical analyses will be generated using PhoenixTM WinNonlin® (Version 6.4 or higher) or SAS (Version 9.4 or higher). PK concentration data will be summarized by analyte, treatment group (cohort, subcohort) at each nominal sample time. PK parameter data will be summarized by analyte and treatment group (cohort, subcohort).

Treatment group (cohort, subcohort) labels will be displayed as follows:

- 1.5 mg/kg DNM2
- 1.5 mg/kg MTM1
- 1.5 mg/kg Overall
- 4.5 mg/kg DNM2
- 4.5 mg/kg MTM1
- 4.5 mg/kg Overall

9 mg/kg DNM2  
9 mg/kg MTM1  
9 mg/kg Overall  
Overall

Summary tables will be presented by the above groups. Overall group will not be displayed in the PK tables.

Listings will be sorted in the following order treatment group (cohort, subcohort), subject, parameter, and visit unless otherwise stated. All data will be listed.

Continuous variables will be summarized by the number of observations, mean, standard deviation, median, minimum and maximum values. Summaries for PK concentrations and AUCs and  $C_{max}$  will be including additionally %CV, geometric mean, geometric SD and geometric %CV.

Categorical variables will be summarized by presenting the frequency and percent. Percentages will be based on the number of non-missing observations or the subject population unless otherwise specified. For each variable, all categories will be shown. Zero frequencies (but not the percent) within a category will be presented.

### 6.3.1 Decimal Places

Decimal places for derived data described in section 6.2 will be determined by the scale of measurement unless otherwise stated. No decimal places will be displayed if the smallest calculated value is  $\geq 100$ ; 1 decimal place will be displayed when the smallest value is within the interval (10, 100), with 10 being inclusive; 2 decimal places will be displayed when the smallest value is within (1, 10), with 1 being inclusive; and so on for even smaller scales of measurement.

Derived data where it is known in advance the result will be an integer for example day, month, year, number of days and total scores (for rating scales) will be presented with zero decimal places.

Means, medians and percentiles will be displayed to one more decimal place than the data, dispersion statistics (e.g. standard deviation) will have two more decimal places, and the minimum and maximum will be displayed to the same number of decimal places as reported in the derived data. Percentages will be displayed with one decimal place. CV% will be reported to 1 decimal place.

P-values will be quoted to 4 decimal places. P-values  $< 0.001$  will be presented as  $p < 0.001$ . Where this value is less than 0.05, 0.01 or 0.001, attention will be drawn to this fact using the conventional “\*”, “\*\*” or “\*\*\*” annotation, respectively.

## 6.4 Subject Disposition

Subject disposition will be summarized by treatment group (cohort, subcohort) and overall. Subject disposition will be summarized as follows:

- Screening failures: The number of subjects who failed screening and the reasons for failure will be tabulated for all subjects.
- Analysis sets: The number of subjects in Pre-Screened Set, Screened Set, Safety Analysis Set, Pharmacokinetic Set.
- Enrollment by region, country and clinical investigator: The number of subjects enrolled in each region, country and clinical investigator.
- Cumulative proportion of information: The number of subjects completing each visit.
- Subject disposition: The number of subjects completing study and early withdrawals including reason for withdrawal and time to withdrawal.
- Inclusion/exclusion criteria: The number of subjects not meeting all inclusion/exclusion criteria.
- The impact of the COVID-19 will be evaluated as follows:
  - Screening failures related to COVID-19
  - Early withdrawals related to COVID-19
  - Visits/Assessments Affected by COVID-19.

If needed, the impact of COVID-19 will be further evaluated based on the above summaries. This might include more detailed summaries how COVID-19 affected visits/assessments and study endpoints.

All disposition data will be listed.

## 6.5 Protocol Deviations

A listing of protocol deviations will be provided within Appendix 16.2.

## 6.6 Baseline Comparability

The comparability of treatment groups with respect to subject demographics and baseline characteristics will be assessed in a descriptive manner, but no formal statistical testing will be performed.

Standard continuous (n, mean, SD, median, min, max) or categorical (frequencies and percentages) variable summaries will be presented by treatment group (cohort, subcohort) for the following variables based on the Safety Analysis Set:

- Age in years
- Gender
- Race
- Ethnicity
- Height (cm)
- Weight (kg)
- BMI (kg/m^2)
- Fertility status for female subjects.

All baseline data will be listed.

## **6.7 Medical History Related to CNM**

Separate tabulations of medical history related to CNM disease at screening will be presented by treatment group (cohort, subcohort) and overall for the Safety Analysis Set. Conditions will be presented by Medical Dictionary of Regulated Activities (MedDRA) primary system organ class and preferred term in descending order in overall group and then alphabetically.

All medical history data will be listed.

## **6.8 Medical History Unrelated to CNM**

Separate tabulations of medical history not related to CNM disease at screening will be presented by treatment group (cohort, subcohort) and overall for the Safety Analysis Set. Conditions will be presented by Medical Dictionary of Regulated Activities (MedDRA) primary system organ class and preferred term in descending order in overall group and then alphabetically.

All medical history data will be listed.

## **6.9 Prior and Concomitant Medications**

Separate tabulations will be produced for prior and concomitant medications presented by treatment group (cohort, subcohort) and overall for the Safety Analysis Set. Prior medications are defined as all medications ending before the date of first dose of study drug. Concomitant medications are defined as medications taken on or after the date of first dose of study drug. Concomitant medications will be summarized using ATC Level 2 and preferred term in descending order in overall group and then alphabetically.

All medication data will be listed.

### **6.10 Exposure to Study Drug**

Extent of exposure (number of days of exposure to study drug) will be presented by treatment group (cohort, subcohort) for the Safety Analysis Set and separately for SAD and MAD parts.

Additionally, number of doses will be summarized.

All dosing information will be listed.

### **6.11 Treatment Compliance**

Treatment compliance will be presented by treatment group (cohort, subcohort) for the Safety Analysis Set and separately for SAD and MAD parts.

All dosing information will be listed.

### 6.12.1 Analysis of dose proportionality

The dose proportionality will be assessed by comparing dose-normalized Cmax and dose-normalized AUClast or AUC∞, single or multiple doses in all cohorts, where possible.

### 6.12.2 Anti-Drug Antibodies

The impact of immunogenicity (anti-drug antibodies, ADA) on the PK of DYN101 will be explored. Blood samples for determination of ADA will be taken in the MAD part and the MAD extension part at the time points specified in the Trial Schedules.

Descriptive statistics (n, mean, SD, median, min, max) of the observed values will be presented by treatment group (cohort, subcohort) and visit for each parameter.

All data will be listed.

### 6.12.3 Metabolic Profiling blood/urine

Blood samples for metabolic profiling of DYN101 will be taken in MAD Week 12 at 2 and 168 hours post-dose.

Urine for metabolic profiling will be collected in MAD Week 12 by collecting urine over a 24-hour interval starting at the same time with the infusion.

Descriptive statistics (n, mean, SD, median, min, max) of the observed values will be presented by treatment group (cohort, subcohort) and visit for each parameter.

All data will be listed.

## **6.13 Pharmacodynamic and Exploratory Efficacy Analyses**

### **6.13.1 PROMIS Questionnaire**

Patient-Reported Outcomes Measurement Information System (PROMIS®) is a National Institutes of Health Initiative, created to assess patient-reported health status for physical, mental, and social well-being to reliably and validly measure patient-reported outcomes in chronic diseases for clinical research and practice. The PROMIS domains tested in this trial are Anxiety (8 items), Depression (8 items), Fatigue (8 items), Pain Interference (8 items), Ability to Participate (8 items) and Physical Function (10 items).

Descriptive statistics (n, mean, SD, median, min, max) for observed values and changes from baseline in T-scores will be presented by treatment group (cohort, subcohort) at each visit for each domain score.

All data, including responses to questionnaire items and T-scores, will be listed.

### **6.13.2 CGI-I Questionnaire**

Clinical Global Impression of Improvement (CGI-I) is a 7-point scale ranging from (1) very much improved to (7) very much worse and is used to assess global changes in the subject's condition compared to the condition before treatment.

Frequency tables for observed values will be presented by treatment group (cohort, subcohort) at each visit. As the questionnaire collects information in relation to the condition before treatment, there is no need to summarize change from baseline.

Additionally, CGI-I responders will be summarized where responder is defined as subject responding 'Very Much Improved' or 'Much Improved'.

All CGI-I data will be listed.

### **6.13.3 PGI-C Questionnaire**

Patient Global Impression of Change (PGI-C) is a scale similar to the CGI-I. It is a 7-point scale ranging from (1) very much improved to (7) very much worse and needs to be completed independent of the investigator who completes the CGI-I.

Frequency tables for observed values will be presented by treatment group (cohort, subcohort) at each visit. As the questionnaire collects information in relation to the condition before treatment, there is no need to summarize change from baseline.

Additionally, PGI-C responders will be summarized where responder is defined as subject responding 'Very Much Improved' or 'Much Improved'.

All PGI-C data will be listed.

#### 6.13.4 GAS Questionnaire

Goal Attainment Scaling is an instrument that is intended for individual evaluation of an intervention. It allows subjects to set individual goals, together with their physician. The number of goals and the content of these goals may differ per subject, but the attainment of the goals is measured in a standardized way. This makes a standardized evaluation of an intervention possible, even when the subjects are all in a different stage of their disease.

Frequency tables for observed values ('YES - MUCH BETTER', 'YES - A LITTLE BETTER', 'YES - AS EXPECTED', 'NO - PARTIALLY ACHIEVED', 'NO - SAME AS BASELINE', 'NO - WORSE') will be presented by treatment group (cohort, subcohort) at each visit.

Additionally, GAS responders will be summarized where responder is defined as subject responding 'YES – MUCH BETTER', 'YES – A LITTLE BETTER').

All GAS data will be listed.

#### 6.13.5 Respiratory Function Tests

Assessment of the respiratory function will be performed with a handheld device.

Descriptive statistics (n, mean, SD, median, min, max) of the observed values and change from baseline (continuous data) will be presented by treatment group (cohort, subcohort) and visit for each parameter. For summary tables the best result will be selected. All collected data will be included in the listings.

Continuous parameters:

- FVC (L)
- %FVC Predicted
- FEV1 (L)
- %FEV1 Predicted
- FEV1/FVC
- MEP (cm H2O)
- %MEP Predicted
- MIP (cm H2O)
- %MIP Predicted
- Oxygen Saturation (%).

For the abbreviated CSR reporting only FVC and MIP will be included.

Respiratory function (Normal; Abnormal NCS, Abnormal CS) will be summarized by treatment group (cohort, subcohort) and period in a shift table from baseline to the worst recorded result in each trial period.

All data, including details of clinically significant findings will be listed.

### **6.13.6 Muscle Strength and Function Tests**

#### **MyoGrip**

MyoGrip is an extremely sensitive tool to measure muscle strength in severely disabled subjects where current tools are unable to measure changes or benefit. For disorders such as CNM, the ability to use the joystick of their electric wheelchair or other fine motor functions is important to the subject. These sensitive measures can also assist in detecting early signals of efficacy of administered drug.

For MyoGrip reporting only the best strength test result will be summarized. Descriptive statistics (n, mean, SD, median, min, max) of the observed values and percent change from baseline will be presented by treatment group (cohort, subcohort) and visit for each parameter.

All data, including all strength test repeats, will be listed.

#### **Motor Function Measure (MFM)**

Motor Function Measure (MFM) is classically used as a measure of functional capacities in subjects with neuromuscular disorders. The MFM 32-item list (MFM32) is a scale to enable an objective assessment of the motor abilities of subjects with neuromuscular diseases whatever the motor function deficiency. Three dimensions are taken into account: D1: standing position and transfers, D2: axial and proximal motor function, and D3: distal motor function.

Descriptive statistics (n, mean, SD, median, min, max) of the observed values and change from baseline will be presented by treatment group (cohort, subcohort) and visit for the following parameters:

- D1 Standing and transfers (%)
- D2 Axial and proximal motor function (%)
- D3 Distal motor function (%)
- Total MFM32 Score (%).

For the abbreviated CSR reporting only Total MFM32 Score will be included.

All data, including responses to questionnaire items and total scores, will be listed.

### **6.13.7 Dysphagia Questionnaire**

Descriptive statistics (n, mean, SD, median, min, max) of the observed values and change from baseline will be presented by treatment group (cohort, subcohort) and visit for the EAT-10 score. All data, including responses to questionnaire items and total scores, will be listed.

### **6.13.8 Muscle Biopsy**

Descriptive statistics (n, mean, SD, median, min, max) of the observed values and change from baseline will be presented by treatment group (cohort, subcohort) and visit.

All data will be listed.

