3.2.5 Rationale for Choice of Doses, Route of Administration and Dosing Regimen

Dose selection was based on the following data/assumptions:

1. Safety profile of DYN101 derived from Cynomolgus monkey studies.
2. Target knock-down: 30 to 50% knock-down of *DNM2* mRNA resulted in a significant reduction of myopathic features in mice. It is assumed that a similar target knock-down level in humans would translate into clinically meaningful effects.
3. Translatability of effective concentrations: the required effective concentration in human tissue (muscle) is expected to be the same as the observed effective concentration in transgenic mouse tissue expressing human *DNM2*.
4. Translation of effective concentrations in humans into doses can be extrapolated from non-human primate data.

See the latest version of the IB for the supportive information on dose selection ([Dynacure](#)).

The minimal recommended starting dose (MRSD) is 1.5 mg/kg (i.e. low dose level in this trial). This MRSD is selected based on the no observed adverse effect level (NOAEL) of 10 mg/kg from a Good Laboratory Practice (GLP), 13-week toxicity study with an 8-week recovery period in Cynomolgus monkeys. The most noteworthy finding during the 13-week treatment was a marked platelet reduction in two female monkeys at 30 mg/kg. This type of platelet change has occasionally been observed in monkeys treated with ASOs of similar chemistry, where a small proportion of individual animals appear to be susceptible to marked effects on platelet counts following ASO treatment. Platelet counts will be closely monitored in this trial to ensure subjects' safety and mitigate the risk. In addition, recovery of platelet counts occurs after drug withdrawal and/or treatment with steroids. Moreover, sudden decreases in platelets have not been observed in humans so far with other constrained ethyl ASOs at dose levels of 1.5 mg/kg.

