In addition, a human dose of 1.5 mg/kg has the possibility to provide a beneficial effect (on-target) to patients with this life-threatening, rare disease. Since this first-in-human study will not be conducted in healthy volunteers, but in patients with a severely debilitating disease, a possible benefit also at the lowest dose level is desired if patients' safety is ensured. Preclinical data in mouse models of XLCNM and ADCNM suggest that therapeutic efficacy might be seen at 15% target knock-down. Based on quadriceps tissue concentration data derived in NHP, this level of knock-down could be achieved after administration of 1.5 mg/kg in humans.

The suggested middle dose level will be 4.5 mg/kg and the high dose level will be up to 9 mg/kg. These dose levels should be sufficient to achieve the target knock-down *DNM2* mRNA levels of 30% and 50%, respectively (based on animal data from quadriceps muscle tissue) ([Table 1](#)). The predicted *DNM2* mRNA knock-down of 30% to 50% is anticipated to be efficacious in humans. Moreover, these target knock-down levels have not raised any safety concerns in nonclinical studies, as reduction of *DNM2* mRNA and *DNM2* protein by more than 80% in key tissues such as liver and skeletal muscle was safe and well tolerated in mice. In addition, 9 mg/kg is below the NOAEL of 10 mg/kg, as derived from the GLP, 13-week toxicity study with an 8-week recovery period in Cynomolgus monkeys.

Table 1: Calculated Weekly Human Dose*

Level of mRNA Knock-down		15%	30%	50%
Muscle	Concentration in NHP Muscle ($\mu\text{g/g}$) ^{a)}	Human Dose (mg/kg) ^{b)}		
Quadriceps at 25 mg/kg SC	9.3±0.8	1.9	4.2	9.7
Quadriceps at 30 mg/kg IV	9.8±2.9	2.1	4.7	11.1

* Based on [Kim, 2018](#).

- Data from a 12-week NHP study at 25 mg/kg SC (non-GLP; [Kim, 2018](#)) and a 13-week toxicity study with an 8-week recovery period in NHP at 30 mg/kg IV ().
- In a humanized, transgenic *DNM2* mouse model, effective DYN101 concentrations in quadriceps muscle were 3.62, 1.55, and 0.7 $\mu\text{g/g}$, respectively at EC₅₀, EC₃₀, and EC₁₅ on mRNA knock-down. These concentrations were used to calculate the human doses required to reach a level of KD of 50%, 30%, and 15% respectively.

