6.2.6 Muscle Biopsy

Muscle biopsies will be performed at the time points defined in the [TRIAL SCHEDULES](#). Details will be described in the Site Operations Manual.

Muscle ultrasound imaging of both the vastus lateralis and biceps brachii will be performed at screening to determine which muscle should be biopsied. This imaging should not be older than 6 months at baseline, otherwise it should be repeated. Muscle biopsies should be obtained from the vastus lateralis according to the site's standard practice (open or needle biopsy) if sufficient muscle mass is identified after ultrasound imaging and muscle depth and location allow. In the event inadequate muscle tissue is identified in the vastus lateralis after ultrasound imaging, or it is determined that the location of a suitable vastus lateralis muscle is not easily accessible, a biopsy should be obtained from the biceps brachii (open or needle biopsy). For subjects undergoing an open muscle biopsy, general anesthesia can be applied. There should be 24 hours between the muscle biopsy and the IMP administration.

Platelet counts need to be verified before a muscle biopsy is performed (the samples for verification of the platelet counts cannot be older than 3 days). The muscle biopsy should be the last assessment at the visit. Platelet counts will need to be verified again before IMP administration (local assessment) only if the previous platelet count is more than 3 days old.

The level of *DNM2* mRNA as well as the concentration of DYN101 will be measured. This evaluation will allow for a measure of target engagement (i.e. the amount of decrease of *DNM2*) and will support the start of the MAD3 cohort and a dose selection for further clinical trials based on the PK/PD modelling, in addition to preclinical data, and results of some of the exploratory efficacy assessments.

In addition, a section of the muscle will be prepared for histology.

In case sufficient muscle biopsy material is left, the material will be stored for further exploratory research (see Section 10.4.4).

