9.10 Pharmacodynamics/Exploratory Efficacy Analyses

Descriptive statistics (arithmetic mean, geometric mean, SD, %CV, median, minimum and maximum) will be used to summarize the PD/exploratory efficacy data. Changes from baseline (where applicable) will also be tabulated.

Advanced analyses and models will be used to summarize in a more effective way the potential effect of the treatment and are not aimed for inferential purposes since the trial is not powered for that purpose.

For the respiratory function and the muscle strength and function tests data available from the NHS or the run-in period, an appropriate mixed effect model for repeated measurements will be applied to all the data to evaluate the evolution over time on a subject basis and to compute the

probability to observe the data under treatment assuming a normal disease progression. The model will include necessary covariates such as dose, demographic data, mutated gene, and biomarker values. Depending on the test, transformations may be applied to the results to ensure use of the appropriate model. For tests providing bounded scores, the normalized data between 0 and 100% will be evaluated using a Beta sampling distribution. For unbounded scores, logarithmic transformations will be applied by default since these are strictly positive values. The selection of covariates such as demographic data and biomarker value will be made using quality of fit criteria such as Akaike Information Criteria.

The analysis of the blood biomarker data will be explorative and will not be performed as part of this trial.

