#### 3.2 Secondary Endpoints

- Comparison of means for PK parameters of DYN101 in plasma ( $AUC_{\tau}$ ,  $AUC_{last}$ ,  $AUC_{\infty}$ ,  $R_{ac(AUC)}$ ,  $R_{ac(C_{max})}$ ,  $C_{max}$ ,  $C_{av SS}$ ,  $CL$ ,  $\lambda_z$ ,  $t_{1/2}$ ,  $t_{max}$ ,  $V_z$ ) by dose (cohort), for single and multiple administration, and by mutated gene (subcohort) and overall using the Pharmacokinetic Set.
- Comparison of geometric means for PK parameters of DYN101 in plasma ( $C_{max}$  and AUCs) by dose (cohort), for single and multiple administration, and by mutated gene (subcohort) and overall using the Pharmacokinetic Set.
- Comparison of means on DNM2 mRNA levels and DYN101 concentrations using muscle biopsy data by dose (cohort), after multiple administration, and by mutated gene (subcohort) and overall using the Pharmacokinetic Set.
- Comparison of mean change from baseline in vital signs, laboratory data and ECG by dose (cohort), for single and multiple administration, and by mutated gene (subcohort) and overall using the Safety Analysis Set.

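### DNM2 mRNA in muscle is planned only as simple change from baseline, although the protocol states its target-engagement levels as percent knock-down

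*SAP*

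**What the plan says.** SAP 6.13.8 plans n, mean, SD, median, minimum and maximum "of the observed values and change from baseline will be presented by treatment group (cohort, subcohort) and visit". It names no variable or unit, and SAP 6.2 gives no derivation for biopsy data. The secondary endpoint in SAP 3.2 reads "Comparison of means on DNM2 mRNA levels and DYN101 concentrations using muscle biopsy data by dose (cohort), after multiple administration", so means of observed levels are part of the endpoint itself.

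Two other places use a relative or geometric scale. For MyoGrip the same SAP plans statistics "of the observed values and percent change from baseline will be presented by treatment group (cohort, subcohort) and visit for each parameter". Protocol 9.10 says: "Descriptive statistics (arithmetic mean, geometric mean, SD, %CV, median, minimum and maximum) will be used to summarize the PD/exploratory efficacy data". The geometric mean and %CV are not carried into SAP 6.13.8, and SAP section 10 does not list this among the changes from the protocol.

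The dose rationale in protocol 3.2.5 is in percent knock-down throughout. On the 30 to 50% reduction seen in mice: "It is assumed that a similar target knock-down level in humans would translate into clinically meaningful effects". On the middle and high dose levels: "mRNA knock-down of 30% to 50% is anticipated to be efficacious in humans". On the low level: "therapeutic efficacy might be seen at 15% target knock-down". Protocol 6.2.6 says that the biopsy evaluation "will support the start of the MAD3 cohort and a dose selection for further clinical trials", through PK/PD modelling together with other evidence. SAP section 12 marks the biopsy table, 14.2.9.1, for the fourth IDMC meeting.

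**The concern.** The expected effect is relative to each subject's own level, and the planned change is in absolute units. The same percent knock-down gives a large change in a subject with high baseline mRNA and a small one in a subject with low baseline mRNA. The mean and SD of change therefore mix the drug effect with baseline spread. Baselines may well differ: biopsies can come from either of two muscles (protocol 6.2.6), and the overall column for each dose pools two mutations.

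At stake is whether a secondary endpoint, which is also an IDMC input, can be set directly against the 15%, 30% and 50% that justified the dose levels, with an honest statement of its uncertainty at about 6 subjects per dose.

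**Working it through.** **1. Is dose selection tied to percent knock-down?** Table 1 of protocol 3.2.5 gives monkey muscle concentrations of 9.3 µg/g at 25 mg/kg SC and 9.8 µg/g at 30 mg/kg IV. Its footnote gives effective concentrations of 0.7, 1.55 and 3.62 µg/g for 15%, 30% and 50% knock-down. With dose = monkey dose × effective concentration / monkey muscle concentration:

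| Row | 15% | 30% | 50% |
|---|---|---|---|
| SC, computed | 25×0.70/9.3 = 1.88 | 25×1.55/9.3 = 4.17 | 25×3.62/9.3 = 9.73 |
| SC, stated | 1.9 | 4.2 | 9.7 |
| IV, computed | 30×0.70/9.8 = 2.14 | 30×1.55/9.8 = 4.74 | 30×3.62/9.8 = 11.08 |
| IV, stated | 2.1 | 4.7 | 11.1 |

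All six reproduce, so the calculation runs from percent knock-down to dose.

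**2. What does a mean change say?** The documents give no mRNA levels or variances, so everything from here is illustration. A mean change of -0.30 units is 0.30/2.0 = 15%, 0.30/1.0 = 30% or 0.30/0.6 = 50%, depending on the mean baseline.

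**3. What can be recovered from the planned table?** Group knock-down can be taken as 1 - mean post / mean baseline. This equals Σ(bᵢkᵢ)/Σbᵢ, with bᵢ the baseline and kᵢ the fractional knock-down, so each subject is weighted by baseline. Take six baselines of 0.5, 0.7, 0.9, 1.1, 1.3 and 1.5 (sum 6.0):
- Knock-down rising with baseline (0, 10, 20, 40, 50, 60%): (0 + 0.07 + 0.18 + 0.44 + 0.65 + 0.90)/6.0 = 2.24/6.0 = 37.3%.
- The same values in reverse order: (0.30 + 0.35 + 0.36 + 0.22 + 0.13 + 0)/6.0 = 1.36/6.0 = 22.7%.
- In both cases the mean within-subject knock-down is 30% (SD 23.7 points) and the geometric mean ratio gives 33.5%. The ratio scale does not depend on who had the high baseline.
- If every subject has exactly 30%, the planned change has mean -0.30 and SD 0.11. All of that SD is baseline spread.

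**4. Precision.** Assumptions: true knock-down 40%, independent log-error of 0.15 on each biopsy, lognormal baselines, 200,000 simulated groups per setting. Relative SE of the estimated knock-down:

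| n | Baseline log-SD | Ratio of planned means | Geometric mean ratio |
|---|---|---|---|
| 6 | 0.3 | 13.7% | 13.1–13.2% |
| 6 | 0.5 | 14.5% | 13.1–13.2% |
| 3 | 0.3 to 0.5 | 19.4% to 20.2% | 18.7% to 18.8% |

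Check for the geometric mean ratio at n=6: 0.6 × √2 × 0.15/√6 / 0.4 = 13.0%.

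**5. What would an interval show?** Under the same assumptions the SE of the mean log ratio is √2 × 0.15/√n. For n=6 it is 0.0866; with t = 2.571 the half-width is 0.223, the ratio runs from 0.6/1.249 = 0.48 to 0.6 × 1.249 = 0.75, and knock-down from 25% to 52%. For n=3 (the planned MTM1 maximum) the SE is 0.1225; with t = 4.303 the half-width is 0.527, the ratio runs from 0.35 to 1.02, and knock-down from about -2% to 65%. The planned table would print none of this.

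**6. Reading the change column alone.** With n=6 and no assay error, the chance that a true 30% group shows at least as large a mean change as a true 50% group is under 0.1% at baseline CV 20%, 0.2% at 30%, 3.7% at 50% and 17.1% at 100%. With n=3 and CV 50% it is 10.0%. On the ratio scale, baseline spread alone cannot cause this.

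**The case against.** The strongest reply is that the planned table already holds the answer. It shows observed means by visit, so anyone can divide post by baseline, and steps 3 and 4 show that the result is nearly as precise. With complete pairs, the three SDs would even allow an approximate interval to be worked out. This stands as far as it goes. It does not give the percent change per subject or its spread, it weights by baseline, and the baseline mean may include subjects who never had a second biopsy.

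Four stronger readings are tempting, and the documents do not support them:
- *That MAD3 turns on a percent knock-down criterion.* No threshold or success criterion is written. Protocol 2.4 plans no formal hypothesis test. IDMC4 reviews 12-week safety, PK and biopsy data, and recommendations rest on the totality of the data (protocol 3.1.1).
- *That the planned summary roughly halves precision.* The mean absolute change has a relative SE of 23% to 30% under the step 4 assumptions (n=6), but that is an unscaled difference. Setting it beside 13% for a knock-down compares unlike quantities.
- *That the two mutations are confounded.* SAP 6.3 gives DNM2 and MTM1 separate columns at each dose; only the overall columns pool them.
- *That the variable is certainly on the wrong scale.* The mRNA unit is not stated. If values were already expressed relative to the subject's own baseline, the change would be percentage points of knock-down. What can be said is that percent change is not specified.

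**Conclusion.** The point holds as a specification gap. The relative scale on which protocol 3.2.5 sets its target-engagement levels is missing from the planned biopsy summary, and so are the geometric statistics that protocol 9.10 promises. A group knock-down can be approximated from the planned means, at a cost in relative SE of about 0.5 to 1.5 percentage points at n=6. The real losses are the within-subject spread, the interval, and protection against a shift when knock-down is related to baseline; in the worked example that shift is about 7 points either side of 30%. These sizes rest on assumed baseline levels, baseline spread and a 15% assay error.

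The practical effect is small. SAP sections 7 and 8 record that the trial was terminated before the interim analysis and that the planned primary and final analyses will not be performed. SAP section 10 limits final reporting to the IDMC outputs and four efficacy parameters, none of which is the biopsy. The biopsy listing (16.2.6.9) is struck out, while table 14.2.9.1 carries no visible strikethrough in the text available. Termination lowers the urgency; it does not make simple change the right summary.

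**What to change.** For DNM2 mRNA only:
- In SAP 6.2 and 6.13.8, define the within-subject ratio of the post-treatment to the baseline level, and state the mRNA unit and how it is normalised.
- Add to table 14.2.9.1, by dose and mutation: the geometric mean ratio, percent knock-down = 100 × (1 - ratio) with its 95% CI from the log scale, and the individual values.
- Keep the observed-value summaries for mRNA and for muscle DYN101 concentration, because the secondary endpoint names their means. Do not apply the ratio to the concentration, where a pre-dose denominator has no meaning.

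The cost is one derived variable and a few table rows. No new data are needed.
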